### 10 Safety Monitoring and Reporting

### 10.1 **Definition of Adverse Events and Reporting Requirements**

#### 10.1.1 **Adverse Events**

The Investigator is responsible for reporting all AEs that are observed or reported during the study, regardless of their relationship to study medication or their clinical significance. Given the potential for protracted time between a subject providing informed consent and organ transplant, AE collection will commence once a subject has provided consent and has at least one invasive study procedure completed and/or performed (e.g., blood draw).

An AE is any untoward medical occurrence in a study subject administered an investigational product which does not necessarily have a causal relationship with the product. An AE can therefore be any unfavorable and unintended sign (including a new, clinical important abnormal laboratory finding), symptom, or disease, temporally associated with the product, whether or not related to the product.

Pre-existing diseases or conditions will not be considered an AE unless there is an increase in the frequency or severity, or a change in the quality of the disease or condition (worsening of a pre-existing condition is considered an AE).

The occurrence of AEs must be sought by non-directive questioning of the subject at each visit during the study. AEs also may be detected when they are volunteered by the subject during or between visits or through physical examination findings, laboratory test findings, or other assessments.

Page 75 of 117 Protocol TCD601B102 (2.0) Confidential

AEs must be recorded under the signs, symptoms, or diagnosis associated with them, and accompanied by the following information: Assessment and grade according to the CTCAE criteria (version 5.0 or higher)

• Relationship to the study treatment

If the event is due to lack of efficacy or progression of underlying illness (i.e., progression of the study indication) the assessment of causality will usually be 'Not suspected.' The rationale for this guidance is that the symptoms of a lack of efficacy or progression of underlying illness are not caused by the trial drug, they happen in spite of its administration and/or both lack of efficacy and progression of underlying disease can only be evaluated meaningfully by an analysis of cohorts, not on a single subject

- Duration (start and end dates) or if the event is ongoing, an outcome of not recovered/not resolved

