#### **10.1.2. Adverse Events**

Each AE and SAE term will be recorded as a verbatim term on the case report forms (CRFs). All AEs and SAEs will be coded by primary system organ class (SOC) and mapped to a preferred term using the MedDRA dictionary (version 26.0 or higher). The investigator will assess AE severity and relationship to the study treatment.

All AEs will be listed. However, only treatment emergent adverse events (TEAEs) will be included in the AE summaries. A TEAE is defined as any AE with an onset date on or after the first study treatment dosing date. In addition, any AEs that the investigators deem to be treatment related, regardless of onset date, will also be considered TEAEs and will be included in the AE summaries.

For the purpose of calculating treatment emergence and inclusion in summary tables, incomplete onset dates will be imputed using the method described in Appendix A.

AEs will be summarized by the number and percentage of subjects in each primary SOC and preferred term. Subjects will be counted only once for each primary SOC and each preferred term. Summary tables of AEs by primary SOC, preferred term and severity will be provided. If a subject has more than one AE coded to the same preferred term, the subject will be counted only once for that preferred term by using the event with the highest severity. Similarly, if a subject has more than one AE within a primary SOC category, the subject will be counted only once in that SOC category by using the event with the highest severity. AEs by primary SOC, preferred term and relationship to study drug will be provided as well. If a subject has more than one AE coded to the same preferred term, the subject will be counted only once for that preferred term by using the most related event. Similarly, if a subject has more than one AE within a primary SOC category, the subject will be counted only once in that primary SOC category by using the most related event. In addition, serious adverse events (SAEs) by primary SOC and preferred term will be provided. Deaths and SAEs will be summarized similarly to AEs. All adverse event tables will also include the total number of events, counting multiple events per subject.

In the AE summary, preferred terms within each SOC will appear in alphabetical order.

Frequencies for deaths and hospitalizations will also be summarized by treatment group and overall.

All information obtained on AEs will be displayed by treatment group.

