#### **For Adverse Events**

If onset date is completely missing, onset date is set to date of randomization.

If (year is present and month and day are missing) or (year and day are present and month is missing):

- If year = year of randomization, then set month and day to month and day of randomization
- If year < year of randomization, then set month and day to December 31.
- If year > year of randomization, then set month and day to January 1.

If month and year are present and day is missing:

- If year = year of randomization and
  - If month = month of randomization then set day to day of first dose
  - If month < month of first dose then set day to last day of month
  - If month > month of first dose then set day to first day of month
- If year < year of randomization then set day to last day of month
- If year > year of randomization then set day to first day of month

For all other cases, set onset date to date of randomization.

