#### **For Concomitant Medications**

Start Date: If start date is completely missing and end date is not prior to randomization, then the medication will be classified as concomitant. If start date is completely missing and end date is prior to randomization, then the medication will be classified as prior.

If (year is present and month and day are missing) or (year and day are present and month is missing) then set month and day to January 1. If year and month are present and day is missing then set day to first day of month.

End Date: If end date is completely missing then the medication will be classified as concomitant.

If (year is present and month and day are missing) or (year and day are present and month is missing) then set month and day to December 31. If year and month are present and day is missing then set day to last day of the month.

Note: that if both start and end dates are missing then the medication will be classified as concomitant.

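### SAP Appendix A imputes incomplete AE onset dates without using the recorded stop date, so a screening AE known to have ended before dosing can be tabulated as treatment-emergent

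*SAP*

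**What the plan says.** SAP 10.1.2 defines treatment emergence by date: "A TEAE is defined as any AE with an onset date on or after the first study treatment dosing date". It adds that AEs the investigator considers treatment related are TEAEs whatever their onset date. For deciding treatment emergence and entry into the summary tables, it says that "incomplete onset dates will be imputed using the method described in Appendix A".

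The AE rules in Appendix A (SAP 15.1) include these branches:

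- Onset wholly missing: "If onset date is completely missing, onset date is set to date of randomization".
- Month missing: "If year = year of randomization, then set month and day to month and day of randomization".
- Only the day missing, same year: "If month = month of randomization then set day to day of first dose".
- Anything left over: "For all other cases, set onset date to date of randomization".

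No AE branch mentions the stop date. The medication rules in the same appendix do use the end date in one situation: "If start date is completely missing and end date is prior to randomization, then the medication will be classified as prior".

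On the data side, Protocol 10.1.1 states that "AE collection will commence once a subject has provided consent and has at least one invasive study procedure completed", and it requires start and end dates for each AE. Protocol 3.1 puts screening at Day -28 to Day -1 and defines Day 0 as the day of transplant and first dose. It asks sites to randomize on Day 0 where possible and allows randomization up to 24 hours before transplant.

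**The concern.** AEs enter the database before any induction drug is given, so some will have started and stopped during screening. If the onset date of such an event is incomplete but its stop date precedes dosing, the recorded data already show that it was not treatment-emergent. Appendix A can nevertheless assign it an onset on the dosing date, and SAP 10.1.2 then counts it.

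Counting an event as treatment-emergent when its timing is unknown is a sound conservative convention. Here the timing is known from a field that the protocol requires. AEs and SAEs are primary endpoints, and the AE summaries admit only TEAEs. A pre-treatment event could therefore appear in the siplizumab or rATG incidence.

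**Working it through.** The plan gives no figure to reproduce. The check applies the Appendix A rules and the SAP 10.1.2 definition to AEs that both started and stopped in screening.

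**Example.** First dose 20 June. The AE ran from 5 to 8 June, and its stop date is recorded.

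| Onset as recorded | Randomized 20 June | Randomized 19 June |
|---|---|---|
| Wholly missing | 20 June, TEAE | 19 June, not TEAE |
| Year only | 20 June, TEAE | 19 June, not TEAE |
| June, day missing | 20 June, TEAE | 20 June, TEAE |

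Where the event becomes a TEAE, its imputed onset is 20 − 8 = 12 days after it ended.

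**Share misclassified.** Inputs: screening Day -28 to -1 (Protocol 3.1) and TEAE if imputed onset ≥ first-dose date (SAP 10.1.2). Assumptions: onset is equally likely on each of the 28 days, and first dose on each of 365 dates. The mean lag from onset to dosing is (1 + 28)/2 = 14.5 days. The stop date does not enter, because the rule does not use it.

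- *Wholly missing, randomized on Day 0:* every event is placed on the dosing date, 100%.
- *Year only, randomized on Day 0:* misclassified unless onset fell in the previous calendar year, 1 − 14.5/365 = 0.960, or 96%.
- *Wholly missing or year only, randomized on Day -1:* the imputed date precedes dosing, 0%.
- *Day missing, either timing:* misclassified when onset falls in the dosing month. For a lag of k days, k dosing dates in each of 12 months have their onset in an earlier month. The share is 1 − 12 × 14.5/365 = 1 − 174/365 = 0.523, or 52%.

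Enumeration over every first-dose date in one year gave the same values: 1.000, 0.960 and 0.523 for Day 0; 0, 0 and 0.523 for Day -1. At a month boundary (randomized 30 June, dosed 1 July), the day-missing branch sends a June event to 1 June, so it is not a TEAE. Day-missing events from an earlier month or year go to the end of that month, before dosing, and do no harm.

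**With a stop-date check** the share is 0% in every branch under both timings.

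**Size of one event.** SAP Section 8 gives 8 subjects in each siplizumab arm and 8 in the control arm: 1/8 = 12.5 percentage points on a preferred-term incidence.

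**The case against.** Several conditions must coincide: the AE begins after consent and an invasive study procedure, ends before dosing, lacks part of its onset date, and has a usable stop date. Start and end dates are required for each AE, and missing values are queried (Protocol 13.4.2). Footnote (a) of the Schedule of Assessments lets all screening occur on the day of transplant for deceased donors, so 28 days is a maximum. The analysis is descriptive (SAP 8.0), all AEs are listed, the rule is the same in every arm, and it over-counts rather than hides events. All of this stands and limits the importance of the point. It does not supply the missing check.

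The wording before the list of TEAE tables in SAP 10.1.2, like Protocol 12.5.2, refers to events starting after the first dose rather than on or after its date. On a strict reading, an onset imputed to the dosing date might not count. However, the on-or-after definition is the one SAP 10.1.2 sets out before sending incomplete dates to Appendix A.

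A reader might also infer more than the documents support:

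- *That all three branches always create a false TEAE.* The wholly missing and month-missing branches do so only when randomization and first dose share a date.
- *That negative AE durations will be reported.* SAP 10.1.2 confines the imputed date to treatment emergence and table inclusion, and no AE duration summary is planned.
- *That the medication rules are a full precedent.* Appendix A checks the medication end date only when the start date is wholly missing. SAP 9.4 does define prior medications by stop date, but the partial-date rules do not use it.
- *That 12.5 points is an expected bias.* It is what any one subject contributes in an arm of 8.

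**Conclusion.** The omission is real. The day-missing branch can turn an AE recorded as over before dosing into a TEAE under either randomization timing, apart from the month-boundary case. The wholly missing and month-missing branches do so under the protocol's default of randomizing on Day 0, but not when randomization falls on the previous date. I found no other section that corrects this.

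The 52%, 96% and 100% apply only to screening AEs that ended before dosing and have the stated part of the onset missing; the first two also rest on the even-spread assumption. They are not shares of all AEs. The number of affected events is unknown and probably small. The point is worth correcting because it affects the primary safety tables, the arms are small, and the information needed is already collected.

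**What to change.** Add at the top of the AE rules in SAP Appendix A:

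*If the known stop date (or the latest date consistent with a partial stop date) is before the first-dose date, the imputed onset is set no later than the stop date and the AE is not treatment-emergent, unless the investigator assesses it as treatment related (Section 10.1.2). In all other branches the imputed onset is the earlier of the Appendix A date and the stop date.*

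The exception is needed because an unconditional exclusion would contradict the relatedness provision in SAP 10.1.2. Where the event is ongoing or the stop date is wholly missing, the present rules apply unchanged.

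The cost is two sentences and a small programming change, with no new data. If the SAP can no longer be revised, the same rule can be applied and reported as a deviation in the clinical study report, as the SAP Introduction provides.

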#### **For Concomitant Medications**

Start Date: If start date is completely missing and end date is not prior to randomization, then the medication will be classified as concomitant. If start date is completely missing and end date is prior to randomization, then the medication will be classified as prior.

If (year is present and month and day are missing) or (year and day are present and month is missing) then set month and day to January 1. If year and month are present and day is missing then set day to first day of month.

End Date: If end date is completely missing then the medication will be classified as concomitant.

If (year is present and month and day are missing) or (year and day are present and month is missing) then set month and day to December 31. If year and month are present and day is missing then set day to last day of the month.

Note: that if both start and end dates are missing then the medication will be classified as concomitant.

## **15.2. Appendix B – Special Data Handling Instructions**

In the case that data has been entered which does not follow a clear handling instruction, the following instructions have been agreed upon and will be followed.

1. For cases in which the site has collected a TAC trough sample, but the patient has not yet received Tacrolimus, the site has been instructed to put in a most recent Tacrolimus dosing time of 00:00.
2. For cases in which the subject has received Tacrolimus before collecting a TAC trough sample, however Time of Previous Tacrolimus Dose is unknown, then the time should be recorded as "00:00".
3. If a PCR viral load is below the lower limit of quantification, then the site will record this data as Negative, with the PCR value as Unknown. If the PCR viral load result is negative or 0 at the site, then it should be recorded as Negative and 0.
